All subjects aged 12 years and older, with at least 365 days of data availability before index date (ID) [ID defined as the date of the latest vaccine dose administered] AND data availability from 12/2020 onwards (i.e. the time when the roll-out of the vaccination campaign started) in the respective database will be included.

	Phase II C3-002 – Study Protocol							
	Author(s): [name], [name], [name]				Version: v2.1			
	Dissemination level: Public							

All studies will be carried out comparing the following cohorts, which we defined based on varying degrees of vaccine exposure and period of predominant SARS-CoV-2 variant as shown in Table 1 below.

COVID-19 vaccination history	Cohort number							
	1	2	3	4	5	6	7	8
1 dose only					x			
Complete primary vaccination course (monovalent only)	x	x	x	x		x	x	x
3rd dose, also called 1st booster (monovalent or any of the adapted, bivalent)	x	x	x	x			x	x
4th dose, also called 2nd booster (monovalent or any of the adapted, bivalent)		x						x
4th dose, also called 2nd booster (any of the monovalent)			x					
4th dose, also called 2nd booster (any of the adapted, bivalent boosters)				x				
Study period								
Start of roll-out 4 th dose/2 nd booster onwards	x	x	x	x				
XBB variant or later dominant	x	x	x	x				
Any variant dominant					x	x	x	x

*Cohorts 3 and 4 will only be created for databases where the vaccine product is reliably recorded in addition to vaccine brand.

Outcomes 1-2 will be assessed in cohorts 1-2 (and 3-4 where available), outcomes 3-7 will be assessed in cohorts 5-8.

Unvaccinated groups will not be used as a comparator in our study for vaccine effectiveness research because they may be very different from vaccinated individuals regarding their risk of infection with SARS-Cov-2. This study therefore focusses on the association of varying degrees of vaccine exposure and COVID-19 related outcomes.

Study period:

Period of “start of roll-out 4th dose/2nd booster dose onwards”: from 01/08/2022 - last available data for each database.

Period of “XBB variant or later dominant”: 01/03/2023 - last available data for each database. Note: This period is not covered by any of the data cuts onboarded for DARWIN EU at the time of protocol submission.

Period of “any variant dominant”: 01/01/2021 (when the wider roll-out of the vaccination campaign started) - last available data for each database.

Statistical analyses:

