Country	Name of Database	Justification for Inclusion	Health Care setting	Type of Data (EHR, claims, registries)	Number of active subjects	Feasibility count of outcome/exposure (if relevant)	Data lock for the last update	Contributing to objectives
United Kingdom	CPRD GOLD	Complete records on SARS-CoV-2 infection, Covid-19 vaccination, and outcome events of interest (excl. hospitalization for COVID-19)	Primary care	EHR	3M	Covid-19: 360,198 Comirnaty: 2,822,947 Spikevax: 311,069	01/2023	1-2 for outcome “COVID-19 related death” only, 4-6
The Netherlands	IPCI	Complete records on SARS-CoV-2 infection, Covid-19 vaccination, and outcome events of interest	Primary care	EHR	1.39M	Covid-19: 941,329 Comirnaty: 1,173,104 Spikevax: 463,315	12/2022	1-6
Spain	SIDIAP	Complete records on SARS-CoV-2 infection, Covid-19 vaccination, and outcome events of interest; Include inpatient admission information.	Primary care + linkage to hospital data	EHR	5.8M	Covid-19: 3,865,976 Comirnaty: 6,548,545 Spikevax: 3,371,395	06/2022	1-6

	Phase II C3-002 – Study Protocol	
	Author(s): [name], [name], [name]	Version: v2
		Dissemination level: Public

Clinical Practice Research Datalink GOLD, United Kingdom (University of Oxford)

The Clinical Practice Research Datalink (CPRD) is a governmental, not-for-profit research service, jointly funded by the National Institute for Health and Care Research and the Medicines and Healthcare products Regulatory Agency, a part of the Department of Health, United Kingdom (UK) (<https://cprd.com>). CPRD GOLD¹¹ comprises computerized records of all clinical and referral events in primary care in addition to comprehensive demographic information and medication prescription data in a sample of UK patients (predominantly from Scotland (52% of practices) and Wales (28% of practices). The prescription records include information on the type of product, date of prescription, strength, dosage, quantity, and route of administration. Data from contributing practices are collected and processed into research databases. Quality checks on patient and practice level are applied during the initial processing. Data are available for 20 million patients, including 3.2 million currently registered patients. Approval for this study was granted via the Research Data Governance Process.

Integrated Primary Care Information Project (IPCI), The Netherlands (Erasmus)

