8.8.4 Objective 3: Vaccine effectiveness to prevent COVID-19 related mortality

Objective 3 will assess vaccine effectiveness to prevent all-cause mortality in the 3 months/6 months after discharge from a COVID-19 hospitalisation. This objective will be assessed for SIDIAP and IPCI only, as no information on hospitalisation are available in CPRD.

	Phase II C3-002 – Study Protocol	
	Author(s): [name], [name], [name]	Version: v2.1
		Dissemination level: Public

The following comparisons will be conducted:

- 1st dose vaccinated vs. 2nd dose vaccinated [cohort 5 vs. 6]
- 2nd vaccinated vs. 3rd dose vaccinated [cohort 6 vs. 7]
- 3rd dose vaccinated vs. 4th dose vaccinated [cohort 7 vs. 8]

Study population

The study populations will be derived similar to the inclusion process outlined for objectives 1-2 above, including sequential matching. The following inclusion criteria will be applied:

- At least 365 days of data availability in the respective database
- At least 90days of time elapsed since the previous vaccine dose for the 3rd or 4th vaccine dose
- At least 21days of time elapsed since the previous vaccine dose for the 2nd vaccine dose
- At least 90days of time elapsed since the last record of a clinical diagnosis of COVID-19 or positive SARS-COV-2 test.

Outcomes

For contextualization, we will assess vaccine effectiveness to prevent COVID-19 hospitalization for the mentioned comparisons. The primary study outcome will be COVID-19 hospitalization followed by death within 3 or 6 months from discharge.

Statistical Analyses

Vaccine effectiveness analyses for COVID-19 related mortality following hospital discharge:

Incidence rates will be calculated for the matched cohorts and both outcomes. Cox proportional hazard models will be calculated for each outcome to provide HR. Follow-up will start at index date, i.e. the date of vaccination with respective new dose for matched pairs.

Negative control outcomes will be used as an additional measure to measure potential residual confounding. In the scenario of potential unmeasured confounding being detected by NCO, empirical calibration²⁵ for HR might be considered to minimise bias.

Kaplan Meier plots and/or cumulative incidence plots will be used to illustrate survival analyses.

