8.8.5 Objectives 4-6: Vaccine effectiveness to prevent post-acute COVID-19 complications

Objectives 4-6 evaluate vaccine effectiveness to prevent post-acute COVID-19 complications, namely new onset diabetes and cardiovascular complications, and will be conducted in all 3 databases.

Similar to objective 3, we will compare people with 1st dose vaccination vs. 2nd dose vaccination [cohort 5 vs. 6], 2nd dose vaccination vs. 3rd dose vaccination [cohort 6 vs. 7] and 3rd dose vaccination vs. 4th dose vaccination [cohort 7 vs. 8].

Study population

The study populations will be derived similar to the inclusion process outlined for objectives 1-3 above, including sequential matching. Inclusion criteria will be applied as outline in section 8.8.4 for Objective 3.

For objectives 4 and 5, people with the respective outcomes of interest, i.e. diabetes recorded anytime before their index date will be excluded for the respective objective. For objective 6, an outcome-free washout window of 365days prior to index date will be implemented.

	Phase II C3-002 – Study Protocol	
	Author(s): [name], [name], [name]	Version: v2.1
		Dissemination level: Public

We will require at least 12 months of follow-up after SARS-CoV-2 infection to assess post-acute complications for outcomes 5, 6, and 7. If people die within 12 months after COVID-19 they will contribute patient-time until death to the analyses. Only infections recorded 12 months before the end of data availability will be included.

Outcomes

- SARS-CoV-2 infection [for contextualization]
- SARS-CoV-2 infection + New onset diabetes Type 1 diabetes within 30-365 days after COVID-19
- SARS-CoV-2 infection + New onset diabetes Type 2 diabetes within 30-365 days after COVID-19
- SARS-CoV-2 infection + cardiovascular events (cerebrovascular disorders, dysrhythmias, ischemic and non-ischemic heart disease, pericarditis, myocarditis, heart failure and thromboembolic disease) in the 12 months after a SARS-CoV-2 infection

Vaccine effectiveness analyses for post-acute COVID-19 complications:

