Incidence rates will be calculated for the matched cohorts and for each outcome. Cox proportional hazard models will be calculated for each outcome to provide HR. Follow-up will start at index date, i.e. the date of vaccination with respective new dose for matched pairs. As previous research showed, no relevant difference in effect estimates was seen for post-COVID-19 symptoms when used fine-grey models accounting for death as competing risk compared to Cox regression². We therefore will not account for competing risk in this analysis.

Negative control outcomes and will be used as an additional measure to measure any potential residual confounding. A list of NCOs used in previous vaccine safety and effectiveness studies will be used. In the scenario of potential unmeasured confounding being detected by NCO, empirical calibration²⁵ for HR might be considered to minimise bias.

Kaplan-Meier plots and/or cumulative incidence plots will be used to illustrate survival analyses.

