
11. LIMITATIONS OF THE RESEARCH METHODS

General limitations:

- The study will be informed by routinely collected health care data and so data quality issues must be considered.
- We will use large-scale propensity scores to minimize measured confounding, and NCOs to assess potential residual confounding. However, given the observational nature of our data, we cannot rule out remaining confounding, which could partially account for findings in this study.

Study-specific limitations:

- Mandatory PCR test for people who tested positive in lateral flow home tests were skipped in early 2022. As not all positive home tests were reported and recorded as clinical diagnoses in primary care databases, it is likely that non-severe SARS-CoV-2 infections are underreported after 02/2022. Moreover, underreporting of COVID-19 for asymptomatic case is to be expected. Underreporting of COVID-19 could lead to misclassification of outcomes for Objectives 4-6, namely post-acute COVID-19 complications (diabetes, cardiac events). For objectives 4-6, we require a minimum follow-up time of 12months after SARS-CoV-2 to identify cases of new-onset diabetes and/or cardiovascular complications. With this, only infections recorded before 02/2022 will be included in the study.
- Routine screening has been impacted by the pandemic, and therefore diagnoses of new conditions, e.g. T2DM might have been delayed depending on testing practices.
- COVID-19 related hospitalization is unlikely to be underreported as people are likely to be asked about previous SARS-CoV-2 infections at hospital admission (Objective 3). However, positive COVID-19 test results that occur around hospitalization do not constitute a hospitalization *due to* COVID-19.

	Phase II C3-002 – Study Protocol	
	Author(s): [name], [name], [name]	Version: v2.1
		Dissemination level: Public

We will use the data cuts currently onboarded for DARWIN EU for CPRD, IPCI and SIDIAP. However, none of those is currently covering the period of XBB variant predominance. We therefore designed the study to assess objectives 1 and 2 to start at the time the 4th vaccine doses were made available for people.

MANAGEMENT AND REPORTING OF ADVERSE EVENTS/ADVERSE REACTIONS

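### On the protocol's stated 4th-dose start and data locks, the 12-month infection rule leaves the 3rd-versus-4th-dose comparison in Objectives 4-6 with no admissible event

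*Protocol*

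**What the plan says.** Section 8.8.5 lists three dose comparisons for Objectives 4-6 in all three databases. The last is "3rd dose vaccination vs. 4th dose vaccination [cohort 7 vs. 8". On timing it says: "Follow-up will start at index date, i.e. the date of vaccination with respective new dose for matched pairs". On infections it says: "We will require at least 12 months of follow-up after SARS-CoV-2 infection to assess post-acute complications for outcomes 5, 6, and 7", and "Only infections recorded 12 months before the end of data availability will be included".

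Section 11 states the effect of this rule: "With this, only infections recorded before 02/2022 will be included in the study". It also fixes the study to the data cuts onboarded at the time of writing. Table 8.2.1 gives their locks as 01/2023 for CPRD GOLD, 12/2022 for IPCI and 06/2022 for SIDIAP.

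The one calendar date for the 4th-dose roll-out is in the Abstract (section 3), where that study period runs "from 01/08/2022 - last available data for each database". The cohort table there attaches this period to cohorts 1-4. Cohorts 5-8 carry the any-variant period, which starts on 01/01/2021.

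Objective 3 (section 8.8.4) uses the same dose comparisons in SIDIAP and IPCI only. Its outcome is set as follows: "The primary study outcome will be COVID-19 hospitalization followed by death within 3 or 6 months from discharge".

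**The concern.** An event counts for Objectives 4-6 only if an infection follows the index date and a complication follows the infection. For cohort 7 vs 8 the index date of both members of a pair is the date of the 4th dose, because the non-boostered member takes over the partner's date. The infection must therefore come after the 4th dose and also at least 12 months before the end of data. If 4th doses start less than 12 months before the lock, no infection can meet both conditions, in either arm.

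Outcomes 5-7 are all labelled primary, and this would remove one of their three planned comparisons. CPRD and IPCI would still contribute person-time after a 4th dose, so the incidence rates planned in section 8.8.5 would have a zero numerator produced by the inclusion rule and not by the absence of complications. The protocol carried out this kind of feasibility check for the XBB period (sections 8.3 and 11) but not here.

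**Working it through.** **Inputs.** Locks: Table 8.2.1. The 12-month rule and start of follow-up: section 8.8.5. 4th-dose start of 01/08/2022: Abstract, study period. Minimum dose intervals of 21, 90 and 90 days: sections 8.5 and 8.8.4. First approvals of 08/12/2020 (UK) and 21/12/2020 (EU): Table 8.6.1.1. Locks are given by month only, so the first and last day of each lock month are both used.

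**Step 1: reproduce the protocol's own cutoff.** Cutoff = lock minus 12 months. The latest lock is CPRD, 01/2023, which gives 01/01/2022 to 31/01/2022. This matches the limit of before 02/2022 in section 11, so the rule is being read as the authors read it. The other two databases have earlier cutoffs than section 11 suggests.

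**Step 2: Objectives 4-6, cohort 7 vs 8.** Gap = 01/08/2022 minus cutoff.

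| Database | Lock | Last admissible infection | Gap to 01/08/2022 (days) |
|---|---|---|---|
| CPRD | 01/2023 | 01/01/2022 to 31/01/2022 | 212 to 182 |
| IPCI | 12/2022 | 01/12/2021 to 31/12/2021 | 243 to 213 |
| SIDIAP | 06/2022 | 01/06/2021 to 30/06/2021 | 426 to 397 |

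Every gap is positive, so no infection after a 4th dose is admissible. A cross-check does not need the exact locks. The protocol says that no current cut reaches the XBB period, which starts on 01/03/2023. Every admissible infection therefore precedes 01/03/2022, five months before 01/08/2022.

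**Step 3: drop the stated start and use dose intervals alone.** Earliest 4th dose = first approval + 21 + 90 + 90 = first approval + 201 days.
- UK: 08/12/2020 + 201 days = 27/06/2021, which is before the CPRD cutoff.
- EU: 21/12/2020 + 201 days = 10/07/2021. This is before the IPCI cutoff but after the latest SIDIAP cutoff, 30/06/2021.

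SIDIAP is therefore empty on any reading. CPRD and IPCI are empty on the stated start, and would admit infections only if 4th doses began more than 182 days (about 6 months) or 213 days (about 7 months) earlier than 01/08/2022.

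**Step 4: Objective 3, cohort 7 vs 8.** The 12-month rule does not apply here; the locks do.
- SIDIAP: data end 32-61 days before 01/08/2022, so on the stated start there are no 4th-dose recipients.
- IPCI: 122-152 days lie between 01/08/2022 and the lock, at most about 5 months. A full 6-month window needs discharge by 01/06/2022 to 30/06/2022, before the first 4th dose. A full 3-month window needs discharge by 01/09/2022 to 30/09/2022, which leaves 1-2 months after roll-out.

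**Step 5: SIDIAP, 2nd vs 3rd dose, Objectives 4-6.** Earliest 3rd dose = 21/12/2020 + 21 + 90 days = 11/04/2021. From there to the latest cutoff, 30/06/2021, is 80 days, or 80/7 = 11.4 weeks. This is an upper bound.

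**Step 6: data needed.** Objectives 4-6 need data beyond 01/08/2022 + 12 months = 01/08/2023. A complete 6-month post-discharge window needs data beyond 01/08/2022 + 6 months = 01/02/2023. No current lock reaches either date.

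**The case against.** The strongest objection is that 01/08/2022 is not stated for these cohorts. The Abstract gives it for cohorts 1-4. For Objectives 3-6, Table 7.1 starts follow-up from 01/01/2021, and section 8.8.3 starts weekly matching when a 4th dose became available in the respective country. Table 8.2.1 lists SIDIAP, locked in 06/2022, for Objectives 1-6, which does not fit 01/08/2022 as a hard first date. This stands as a limit: for CPRD and IPCI the conclusion is conditional on the stated start. It does not rescue the plan, because no other 4th-dose date is given. If 4th doses did start early enough, the stated date needs correcting. It does not help SIDIAP.

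A reader might also infer that the six-month Objective 3 outcome is impossible after a 4th dose. The documents do not support that for IPCI. Section 8.8.4 has no completed-window rule, and follow-up ends at the end of observation, so deaths before the lock count and the rest are censored. The result is truncated, not empty.

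The limits are partly disclosed. Section 11 gives the infection cutoff and the reliance on current cuts, and sections 3 and 8.2 foresee a later repetition. What is missing is the consequence for cohort 7 vs 8.

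Finally, a cell without events gives no hazard ratio, adds nothing to the pooled estimate and does not bias the other two comparisons. That is fair. That someone would read the empty cell as absence of effect is speculation, and the point does not depend on it.

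**Conclusion.** The conflict is real. On the protocol's only stated 4th-dose start and its fixed locks, cohort 7 vs 8 can produce no admissible event for Objectives 4-6 in any database. The shortfall is at least 182 days in CPRD, 213 in IPCI and 397 in SIDIAP. Empty here refers to events; person-time after a 4th dose exists in CPRD and IPCI. The SIDIAP result needs only the lock, the EU approval date and the dose intervals. The CPRD and IPCI results also rest on 01/08/2022 applying to cohort 8, so an unconditional claim of emptiness in all three databases would go beyond the documents.

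Two smaller consequences follow. In Objective 3, because of the locks, cohort 7 vs 8 has no 4th-dose recipients in SIDIAP on the stated start and at most about 5 months from dose to data end in IPCI. The Abstract also says that COVID-19 hospitalisation is not available for IPCI, against sections 8.2, 8.8.3 and 8.8.4. If the Abstract is right, this comparison has no usable database. In Objectives 4-6, the 12-month rule leaves SIDIAP at most about 11 weeks for 2nd vs 3rd dose. The documents give no dose counts by date, so how many 3rd doses fall in those weeks cannot be said.

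**What to change.** - For the current data cuts, withdraw cohort 7 vs 8 from Objectives 4-6 and state that it is not estimable, or defer it to a cut extending beyond 08/2023.
- State the 4th-dose start that applies to cohorts 7-8 in each country. If it is earlier than 01/08/2022, correct the date and redo the check above.
- For Objective 3, state that the six-month result for cohort 7 vs 8 is not estimable in SIDIAP and is truncated in IPCI.
- Add a table of database by comparison by objective showing which cells can hold events, including the short SIDIAP window for 2nd vs 3rd dose. Restrict the analyses and the random-effects pooling in section 8.9 to those cells.

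The cost is a protocol amendment and a short feasibility table. The downside is that one planned comparison is withdrawn or delayed until a data refresh.

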Hazard ratios will be calculated for subsequent time windows after index date, i.e. in bi-weekly intervals.

Monthly intervals will be used in case of small event counts to increase sample size and power if needed.

Kaplan-Meier plots and/or cumulative incidence plots will be used to illustrate survival analyses.

Objectives 3-6: Post-acute COVID-19 complications

The following comparisons will be conducted for objectives 3-6:

- First-dose vaccinated vs. second-dose vaccinated [cohort 5 vs. 6]
- Second-dose vaccinated vs. 3rd dose vaccinated (1st booster dose) [cohort 6 vs 7]
- 3rd dose vaccinated vs. 4th dose vaccinated (2nd booster dose) [cohort 7 vs 8]

Objective 3 will be assessed for SIDIAP and IPCI only, whereas objectives 4-6 will be assessed in CPRD, IPCI and SIDIAP.

Study population

The study populations will be derived similar to the inclusion process outlined for objectives 1-2 above, including sequential matching.

For objectives 4 and 5, people with the respective outcome recorded anytime in their history will be excluded for the respective objective. For objective 6, an outcome-free washout window of 365 days prior to index date will be implemented.

Outcomes:

- COVID-19 hospitalization + death within 3/6 months from discharge
- SARS-CoV-2 infection + New onset diabetes Type 1 diabetes within 30-365 days after COVID-19
- SARS-CoV-2 infection + New onset diabetes Type 2 diabetes within 30-365 days after COVID-19
- SARS-CoV-2 infection + cardiovascular events (ccar) in the 12 months after a SARS-CoV-2 infection

	Phase II C3-002 – Study Protocol	
	Author(s): [name], [name], [name]	Version: v2.1
		Dissemination level: Public

For contextualization and interpretation of the study findings, we will also report the number of people with COVID-19 hospitalization and SARS-CoV-2 infections in each group, as these are part of the overall outcomes of “death following discharge from COVID-19 hospitalisation” and post COVID-19 complications.

Vaccine effectiveness analyses for COVID-19 related mortality following hospital discharge:

Incidence rates will be calculated for the matched cohorts and outcome. Cox proportional hazard models will be calculated for each outcome to provide HR. Negative control outcomes will be used as an additional measure to measure residual confounding. In the scenario of potential unmeasured confounding being detected by NCO, empirical calibration²⁵ for HR might be considered to minimise bias.

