7. RESEARCH QUESTION AND OBJECTIVES

Research Question

What is the effectiveness of the EMA-authorized COVID-19 vaccines Comirnaty and Spikevax against severe COVID-19 and post-acute outcomes of SARS-CoV-2 infection?

Objective(s)

To generate additional evidence on the effectiveness of COVID-19 vaccines at preventing severe COVID-19 and post-acute outcomes of SARS-CoV-2 infection.

Specifically, this study has 6 objectives:

1. To assess the effectiveness of COVID-19 vaccination for the prevention of severe COVID-19 related outcomes (COVID-19 related hospitalisation or COVID-19 related death)
2. To assess waning of the effectiveness of COVID-19 vaccination for the prevention of severe COVID-19 related outcomes (COVID-19 related hospitalisation or COVID-19 related death)
3. To assess the effectiveness of COVID-19 vaccination for the prevention of all-cause mortality in the 3- and 6-months following discharge for COVID-19 related hospitalisation
4. To assess the effectiveness of COVID-19 vaccination for the prevention of new-onset type 1 Diabetes Mellitus in the 12 months after a SARS-CoV-2 infection
5. To assess the effectiveness of COVID-19 vaccination for the prevention of new-onset type 2 Diabetes Mellitus in the 12 months after a SARS-CoV-2 infection
6. To assess the effectiveness of COVID-19 vaccination for the prevention of cardiovascular events in the 12 months after a SARS-CoV-2 infection

	Phase II C3-002 – Study Protocol	
	Author(s): [name], [name], [name]	Version: v2.1
	Dissemination level: Public	

Table 7.1: Primary and secondary research questions and objective

A. Primary research question: Objectives 1-2

Objective:	To assess the effectiveness and waning of effectiveness of COVID-19 vaccination for the prevention of severe COVID-19 related outcomes
Hypothesis:	NA
Population (mention key inclusion-exclusion criteria):	All subjects aged 12 years and older, with at least 365 days of data availability in the respective database before index date (ID) with 
 • a 3rd-vaccine dose (1st booster dose) of Comirnaty or Spikevax. • at least 365days of data availability in the respective database • at least 90days of time elapsed since the last vaccine dose (i.e. the 3rd vaccine dose or 1st booster) at the time of study inclusion • at least 90days of time elapsed since the last record of a clinical diagnosis of COVID-19 or positive SARS-COV-2 test at the time of study inclusion.

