Exposure:	4 th vaccine dose/2 nd booster dose of Comirnaty or Spikevax
Comparator:	No 4 th vaccine dose/2 nd booster dose (only 3 rd dose)
Outcome:	COVID-19 related hospitalisation;COVID-19 related death
Time (when follow up begins and ends):	Follow-up start: at index date of matched 3-dose vaccinated/4-dose vaccinated people after start of roll-out of vaccination programs for 2nd booster dose End of follow-up: End of their observation (i.e. date of data extraction, database availability or death), next vaccine dose or outcome event, whatever comes first.
Setting:	Primary care electronic health records from SIDIAP [Spain], IPCI [The Netherlands] and CPRD GOLD [UK]
Main measure of effect:	Vaccine effectiveness, calculated as 1 - Hazard ratio (HR)

B. Primary research question: Objectives 3

	Phase II C3-002 – Study Protocol	
	Author(s): [name], [name], [name]	Version: v2.1
	Dissemination level: Public	

Outcome:	To assess the effectiveness of COVID-19 vaccination for the prevention of post-acute all-cause mortality in the 3- and 6-months following discharge for COVID-19 related hospitalisation
Hypothesis:	NA
Population (mention key inclusion-exclusion criteria):	All subjects aged 12 years and older, with at least 365 days of data availability in the respective database before index date (ID) with 
 • a 1st-vaccine dose [2nd vaccine dose; 3rd vaccine dose] of Comirnaty or Spikevax. • at least 365days of data availability in the respective database. • at least 90days of time elapsed since the last vaccine dose at the time of study inclusion. • at least 90days of time elapsed since the last record of a clinical diagnosis of COVID-19 or positive SARS-COV-2 test at the time of study inclusion.
Exposure:	2 nd vaccine dose [3 rd vaccine dose; 4 th vaccine dose] of Comirnaty or Spikevax
Comparator:	No 2 nd vaccine dose [3 rd vaccine dose; 4 th vaccine dose] of Comirnaty or Spikevax
Outcome:	All-cause mortality within 3/6months following COVID-19 related hospitalisation

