Time (when follow up begins and ends):	Follow-up start: at index date of matched single-vaccinated/ double-vaccinated people [double-vaccinated vs. triple vaccinated; triple vaccinated vs. 4 th dose vaccinated] after start of roll-out of vaccination programs i.e. from 01/01/2021 End of follow-up: End of their observation (i.e. date of data extraction, database availability or death), next vaccine dose or outcome event, whatever comes first.
Setting:	Primary care electronic health records from SIDIAP [Spain], IPCI [The Netherlands] and CPRD GOLD [UK]
Main measure of effect:	
 • Incidence rate for outcomes-100'000 person-years • Vaccine effectiveness against post- acute COVID-19 complications, calculated as 1 - HR

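### Objectives 4-6: the infection-plus-complication outcome can show vaccine effectiveness through fewer recorded infections alone, and no planned analysis shows whether diabetes or cardiovascular events were themselves reduced

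*Protocol*

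**What the plan says.** The objectives are worded as prevention of the complication. For type 2 diabetes, Protocol section 7 reads: "To assess the effectiveness of COVID-19 vaccination for the prevention of new-onset type 2 Diabetes Mellitus in the 12 months after a SARS-CoV-2 infection".

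Section 8.8.5 makes the event a sequence: "SARS-CoV-2 infection + New onset diabetes Type 2 diabetes within 30-365 days after COVID-19". Type 1 diabetes and cardiovascular events are built the same way. On time zero it says: "Follow-up will start at index date, i.e. the date of vaccination with respective new dose for matched pairs". On the model: "Cox proportional hazard models will be calculated for each outcome to provide HR". Everyone in the matched cohorts is therefore at risk from vaccination, not only those who become infected.

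Table 7.1, part C, gives the main measure as "Vaccine effectiveness against post- acute COVID-19 complications, calculated as 1 - HR".

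The protocol is open that infection is a component of the outcome. The Abstract states that "we will also report the number of people with COVID-19 hospitalization and SARS-CoV-2 infections in each group", and section 8.8.5 lists infection as an outcome for context. Section 8.8.6 plans no sensitivity analyses. Negative control outcomes are included to measure residual confounding.

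**The concern.** A diabetes or cardiovascular diagnosis counts if a recorded infection came before it in the window, and does not count otherwise. Background cases that happen to follow a recorded infection are therefore events. The same cases without a recorded infection are not. A dose that lowers infection, or a dose group that is tested less often, has fewer people in whom a background case can count. The composite hazard ratio then falls even if no case of diabetes or cardiovascular disease was prevented.

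At stake is what objectives 4-6 can conclude. A positive result cannot separate fewer infections, or fewer recorded infections, from fewer complications, yet the label reads as effectiveness against the complication.

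**Working it through.** The protocol states no sample size, expected effectiveness or event rates, so there is no figure to reproduce. The structure comes from sections 7 and 8.8.5. Every rate below is an assumption.

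**1. Rate ratio.** In dose group a, let λ_a be the rate of recorded infection and p_a the probability of the complication in the window after infection.

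- Composite rate = λ_a × p_a.
- Ratio between groups = (λ_1/λ_0) × (p_1/p_0) = HR(recorded infection) × RR(complication among the infected).
- If neither vaccination nor infection affects the complication, p_1 = p_0 and composite VE = 1 - λ_1/λ_0 = infection VE. Infection VE of 10, 30, 50 or 70% gives composite VE of 10, 30, 50 or 70%, whatever the diabetes incidence.
- If risk among the infected also falls, with RR 0.8, and infection VE is 30%, composite VE = 1 - 0.7 × 0.8 = 44%.

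**2. First-event Cox model under the same null.** Counting one infection per person uses up susceptible people faster in the comparator group, which pulls the estimate towards zero when infection is common. With a rare complication and no censoring, the result is close to the ratio of two-year infection risks. For infection VE of 30%:

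| Yearly infection risk (comparator) | Two-year risk, comparator | Two-year risk, newer dose | 1 - ratio |
|---|---|---|---|
| 5% | 1 - 0.95² = 0.0975 | 1 - 0.9025^0.7 = 0.0693 | 28.9% |
| 20% | 1 - 0.80² = 0.360 | 1 - 0.64^0.7 = 0.268 | 25.5% |
| 50% | 1 - 0.50² = 0.750 | 1 - 0.25^0.7 = 0.621 | 17.2% |

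A large-sample Cox score equation was solved on a daily grid over 730 days. Assumed inputs were diabetes incidence of 0.5% per year, no censoring or a mean of 180 days to next-dose censoring, and the event dated at infection or at diabetes. Across all scenarios:

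| Infection VE | Composite VE when the effect on diabetes is zero |
|---|---|
| 0% | 0% |
| 10% | 5-10% |
| 30% | 17-30% |
| 50% | 33-50% |
| 70% | 55-70% |

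At infection VE of 30%, yearly infection risk of 5-20% and next-dose censoring, the range is 28-30%. Under the same null, both the RR among the infected and the HR for any new-onset diabetes are 1.00.

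**3. If infection does cause diabetes.** Let infection multiply diabetes risk by R, and let a fraction q of comparators be infected. Relative total diabetes is 1 + q(R - 1) in the comparator group and 1 + q(1 - VE)(R - 1) in the newer-dose group. With infection VE of 30%, the composite rate-ratio VE stays at 30%, while the reduction in all new diabetes is:

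- q = 10%, R = 1.4: 1 - 1.028/1.040 = 1.2% (1.1% if the excess is limited to 335 of 365 days);
- q = 20%, R = 1.4: 1 - 1.056/1.080 = 2.2%;
- q = 20%, R = 2.0: 1 - 1.14/1.20 = 5.0%.

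**The case against.** **The composite is disclosed and fits the stated question.** The objectives refer to the months after an infection, and the label says post-acute COVID-19 complications, not all diabetes. Following everyone from vaccination targets a total effect and avoids conditioning on infection, which occurs after exposure. If infection causes the complication, preventing infection is a genuine route of prevention. This stands, and it is why the composite should be kept. It does not supply evidence that the complications fell, because background cases after infection are counted too.

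**Infection is already analysed.** A reader might infer that only infection counts will be shown. The text does not support that: section 8.8.5 lists infection as an outcome and plans Cox models for each outcome, so an infection HR appears to be planned. What is absent is any outcome that ignores infection status.

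**Existing safeguards.** Section 11 concedes that under-recorded infection can misclassify outcomes for objectives 4-6, and limits these analyses to infections before 02/2022. Section 8.8.3 hopes that negative controls share biases such as healthcare-seeking. These may reduce or reveal part of the testing problem. They cannot reveal a real effect on infection, because that is not confounding.

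**A reader might extend the point to objective 3.** The argument would be that in-hospital deaths are lost and that "All-cause mortality within 3/6months following COVID-19 related hospitalisation" conflicts with "The primary study outcome will be COVID-19 hospitalization followed by death within 3 or 6 months from discharge". The documents do not support this. Death after discharge is the stated objective, the objective row of Table 7.1 part B also says discharge, and section 8.8.4 already plans effectiveness against hospitalisation for the same comparisons.

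**Conclusion.** The point holds for objectives 4-6. An effect on recorded infection alone yields a positive composite VE when diabetes and cardiovascular risk are unchanged, and no planned analysis separates the two.

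Two stronger readings go too far. One is that the composite HR always equals the infection HR: this is exact for the rate ratio but attenuated in a first-event Cox model when infection is common (17-30% at infection VE of 30%, 33-50% at 50%). The other is that results will be misread: they could be, but infection results are to be reported alongside.

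The direction follows from the outcome definition and needs no assumed rates. The sizes rest on assumed infection risks, diabetes incidence, censoring and, in step 3, assumed risk ratios. The statistical analysis plan was not available and might hold further models, but the label is fixed in Table 7.1 and section 8.8.6 states that no sensitivity analyses are planned.

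**What to change.** In section 8.8.5, using the same matched cohorts, prespecify the same Cox model for new-onset type 1 diabetes, type 2 diabetes and cardiovascular events regardless of recorded infection. Report it and the infection HR, each with its confidence interval, beside every composite HR.

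In Table 7.1 part C, describe the composite as effectiveness against recorded infection followed by the complication. State that a reduction in diabetes or cardiovascular disease will be claimed only from the infection-independent outcome.

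Do not adopt a rule that merely asks whether the composite HR is lower than the infection HR. It ignores uncertainty, and the attenuation shown above can move the composite HR towards 1 under the null. If the two are compared, give an interval for their ratio and note that it is a contrast among the infected, and so open to selection.

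The cost is a few extra models per database, brand and dose comparison on cohorts that will already exist. The infection-independent estimates will lie closer to the null.
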